## Study protocol

### Patient population and randomization

The present study included patients for whom COL was planned with 1) cervical myelopathy at 3 or more levels due to spondylosis, congenital stenosis, or OPLL; 2) aged more than 20 years; and 3) with American Society of Anesthesiology physical status class 1 or 2. The exclusion criteria were as follows: 1) concomitant neurological disease such as cerebral palsy or amyotrophic lateral sclerosis; 2) concurrent cancer or infection; 3) previous cervical spinal surgery; 4) a trauma-associated lesion; 5) inability to be followed up; and 6) refusal to participate in the study. The proportions of fusion failure were assumed to 30% and 10% in laminoplasty with a conventional drill and with a UBS. To provide a power of 80% with a two-tailed significance level of 0.05, 72 patients for each surgical method were required. Considering a drop-out rate of 25%, 95 patients in each group were enrolled. A computer-generated variable randomized block design was used for randomization and a research nurse independent of this trial provided randomization with concealed assignment. A total of 190 patients were equally allocated to one of two treatments (Fig. 1). The attending surgeons, patients, and staff members in the operating room were blinded to the surgical method until the day of surgery. Recruitment of patients started in July 2015 and ended in February 2018.

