### Statistical analysis

Continuous data were summarized as mean or median (min, max) values depending on normality. Categorical variables are summarized as frequency (%). The analysis for the primary outcome was performed on data from the intention-to-treat population, which included all subjects who were randomized. Since about 14% of subjects missed the CT to assess bone union at 6 months, multiple imputation was applied. Five multiply-imputed data sets were created using a monotone logistic regression model. The variables in Table 1 were included in the imputation model. A sensitivity analysis was performed with the subjects who received a CT scan at 6 months, who were defined as the per-protocol population. The union rate was compared between the drill group and the UBS group using logistic regression. Because each subject had several laminae, logistic regression with the robust sandwich covariance estimate was used to account for the correlation among laminae within a subject.

Secondary outcomes were compared using the chi-square test for non-continuous values and the t-test or Wilcoxon rank-sum test for continuous values. A linear mixed model was used for clinical outcomes to evaluate between-group differences and changes during each postoperative period compared to the preoperative point, and adjusted p-values were evaluated using the Bonferroni method. The fixed effects were group, time, and the interaction between group and time. All statistical analyses were performed using SAS version 9.4 (SAS Institute, Cary, NC, USA), and statistical significance was defined as  $p < 0.05$  (two-sided).

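### Is the stated 80% power wrong because the trial was sized per patient but the primary analysis is per lamina?

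*Combined protocol and SAP*

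**What the plan says.** Under Patient population and randomization, the planning rates are given as "The proportions of fusion failure were assumed to 30% and 10% in laminoplasty with a conventional drill and with a UBS". The requirement follows: "To provide a power of 80% with a two-tailed significance level of 0.05, 72 patients for each surgical method were required". The allowance for attrition is "Considering a drop-out rate of 25%, 95 patients in each group were enrolled". The only hint at the number of laminae per patient is the eligibility criterion, "cervical myelopathy at 3 or more levels due to spondylosis, congenital stenosis, or OPLL".

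Under Statistical analysis, the primary comparison of union uses several observations per patient: "Because each subject had several laminae, logistic regression with the robust sandwich covariance estimate was used to account for the correlation among laminae". It is run on all randomised patients, with multiple imputation for the roughly 14% who had no 6-month CT.

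**The concern.** The two sections use different units. The sample size counts patients, each contributing one outcome. The primary test counts laminae and allows for their correlation within a patient. The information in that test depends on how many laminae each patient contributes and how strongly they agree, and neither quantity enters the sample-size calculation. The text also leaves open whether 30% and 10% are proportions of laminae that fail or of patients with at least one failed lamina.

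If the difference were large and unfavourable, the trial could have less power than it claims and a null result would be misread. If it were large and favourable, many more patients would have been enrolled than the target needs. The attrition line also looks one patient short, because 95 × 0.75 = 71.25, which is below 72.

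**Working it through.** **Inputs from the documents.** Failure rates 0.30 and 0.10; two-sided 0.05; power 80%; 72 per arm; 25% drop-out; 95 per arm; about 14% missing CT; at least 3 levels per patient.

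**Assumed, because the documents do not give them.** Laminae per patient m = 3 to 5; intra-patient correlation (ICC) from 0 to 1; and, for reading B below, a beta-binomial model with the same ICC in both arms.

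**1. Reproduce 72.** With mean rate 0.20:

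- Uncorrected n = [1.960·√(2·0.2·0.8) + 0.842·√(0.21 + 0.09)]² / 0.2² = 61.6
- Continuity-corrected n = (61.6/4)·[1 + √(1 + 4/(61.6·0.2))]² = 71.25, rounded up to 72

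The uncorrected pooled formula rounds up to 62 and the unpooled one to 59, so 72 matches the corrected per-patient formula. The plan's figure is arithmetically right for its own inputs.

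**2. Attrition.** Applied before rounding, 71.248/0.75 = 94.997, which rounds to the stated 95. Starting from the rounded 72 gives 96, one more per arm. The line needs no correction.

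**3. Power of a lamina-level test.** Effective laminae per arm are n·m/[1 + (m − 1)·ICC]. These go into the uncorrected two-proportion power formula

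Φ{[d − 1.960·√(2·p̄(1 − p̄)/n_eff)] / √[(p₁(1 − p₁) + p₂(1 − p₂))/n_eff]},

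where d = |p₁ − p₂| and p̄ is the mean of the two rates.

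*Reading A: 30% and 10% are lamina rates.* At ICC = 1 the effective size is 72 whatever m is, and power is Φ{(0.2 − 1.960·√(0.32/72))/√(0.30/72)} = Φ(1.074) = 85.9%. Any smaller ICC raises it.

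| Laminae | ICC 0.3 | ICC 0.5 | ICC 0.7 | ICC 1 |
|---|---|---|---|---|
| 3 | 98.7% | 96.2% | 92.5% | 85.9% |
| 4 | 99.3% | 97.1% | 93.3% | 85.9% |
| 5 | 99.6% | 97.6% | 93.7% | 85.9% |

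On this reading, one outcome per patient is the worst case and the sizing is conservative.

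*Reading B: 30% and 10% are the proportions of patients with any failed lamina.* For each m and ICC, the lamina rates are solved so that the beta-binomial probability of at least one failure is 0.30 and 0.10. With 5 laminae and ICC 0.5 they are 0.149 and 0.045; n_eff = 72·5/3 = 120, and power is 77.3%. Power at 72 per arm:

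| Laminae | ICC 0 | ICC 0.3 | ICC 0.5 | ICC 0.7 | ICC 0.9 |
|---|---|---|---|---|---|
| 3 | 87.4% | 81.9% | 81.4% | 82.5% | 84.7% |
| 4 | 87.6% | 79.8% | 79.2% | 81.0% | 84.2% |
| 5 | 87.7% | 77.8% | 77.3% | 79.7% | 83.8% |

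Power falls below 80% only with 4 or 5 laminae and mid-range ICC, and then by no more than about 3 points.

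**4. Power at the number observed.** The trial randomised 95 per arm, and 95 × 0.86 = 81.7 have the 6-month CT. Under reading A, power is then at least 89.9%. Under reading B with 5 laminae and ICC 0.5, n_eff = 81.7·5/3 = 136.2 and power is 82.3%. On a finer ICC grid the minimum is 82.1% (5 laminae, ICC 0.4). No scenario falls below 80%.

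**The case for a change.** The strongest argument for an edit is that calling the design conservative is safe only on the per-lamina reading, which the available text does not confirm. On the per-patient reading the planned 20-point difference is not the quantity the lamina-level test estimates. The corresponding lamina-level difference is then about 5 to 18 points, depending on m and ICC. One stated power figure would cover anything from about 77% to nearly 100% at 72 per arm, and a reader of a null result would want to know which effect, in which unit, the trial could detect. The edit would also be cheap.

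The mismatch of units stands, and so does the absence from the available text of a unit for the rates. However, that text contains no outcome-definition section, and the rates and the 72 are both tied to a cited source, so the unit may be settled elsewhere. The edit would also give no determinable corrected power. An ICC and a laminae count chosen after recruitment would be retrospective, and a null result would in any case be judged by its confidence interval.

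**Conclusion.** No change is needed. The sample size was worked out per patient and the analysis is per lamina, so the stated 80% is a planning approximation rather than the exact power of the primary test. Nothing in the documents shows that it is not achieved. Power at 72 per arm is at least 86% if the rates are per lamina and about 77% to 88% if they are per patient. At about 82 observed per arm the minimum is about 82%.

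These figures rest on 3 to 5 laminae per patient, the ICC range shown, a normal approximation and, for the per-patient reading, an equal-ICC beta-binomial model. They leave out the modest losses from imputation and from unequal numbers of laminae, which could use up the 2-point margin in the least favourable corner.

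The validity of the primary test does not depend on the sample-size paragraph: the robust variance already deals with the correlation among laminae. Spelling out the unit, the cluster size and the ICC would be tidier reporting, but for a trial that has finished recruiting it would move no result.

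### The stated patient blind ends on the day of surgery, so it does not cover the postoperative clinical outcomes, although patients never need to know which device was used

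*Combined protocol and SAP*

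**What the plan says.** The section Patient population and randomization has one sentence on blinding: "The attending surgeons, patients, and staff members in the operating room were blinded to the surgical method until the day of surgery". It names three groups and gives them a single end point. The same section separately describes concealment of the allocation: "a research nurse independent of this trial provided randomization with concealed assignment".

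The Statistical analysis section shows when outcomes are measured. For the primary outcome: "Since about 14% of subjects missed the CT to assess bone union at 6 months, multiple imputation was applied". For the clinical outcomes, the mixed model is used to "evaluate between-group differences and changes during each postoperative period compared to the preoperative point". P-values from that analysis are Bonferroni-adjusted; the number of comparisons is not given.

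The available text does not list the secondary outcomes, does not say which clinical outcomes are patient-reported, and does not describe who read the CTs or who collected the clinical scores.

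**The concern.** A blind that stops on the day of surgery protects what happens before surgery. It does not protect outcomes measured weeks or months later. For surgeons and theatre staff this cannot be avoided, because they handle the device. Patients do not have to know whether a drill or a UBS cut the bone, and the available text gives no reason for ending their blind at the same moment.

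What is at stake is the comparison of clinical outcomes. Patients who believe they had the newer device may rate themselves differently, and staff who know the arm may score them differently. Such a shift falls on one arm and looks like a treatment effect. Randomization, concealed assignment, multiple imputation and the mixed model do not remove it, because it arises in the measurement itself.

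**Working it through.** **1. Timing, side by side.**

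| Item | Where stated | Timing |
|---|---|---|
| End of stated blind: surgeons, theatre staff, patients | Patient population and randomization | Day of surgery |
| Clinical outcomes, compared between groups and with baseline | Statistical analysis | Each postoperative period |
| Bone union on CT (primary) | Statistical analysis | 6 months |

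Both outcome rows fall after the stated end of the blind. No sentence in the available text extends blinding past surgery for anyone.

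**2. Which outcomes patient knowledge can reach.** It can act on clinical outcomes that are patient-reported or otherwise subjective. It should have little direct effect on union read from a CT. There the relevant person is the reader, on whom the available text is silent.

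**3. The plan's own figures.** The plan attaches no figure to blinding. Its sample size does reproduce, though it does not bear on this point. With failure proportions 0.30 and 0.10, two-sided 5% and 80% power, the usual formula gives 62 per group, or 72 with the continuity correction, as stated. For 25% drop-out, 72 / 0.75 = 96, against 95 enrolled.

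**4. Illustrative size for a clinical outcome.** The documents give no bias size, so everything here is assumed except the 95 per arm and the 14% missing. That 14% refers to the 6-month CT and is borrowed for the clinical scores: 0.86 × 95 = 81.7, taken as 82.

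Suppose there is no true difference and knowledge of the arm shifts one arm by b standard deviations. The two-group test statistic then has mean

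λ = b × √(n/2) = b × √41,

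and the false-positive rate is Φ(−c + λ) + Φ(−c − λ), where c is the two-sided critical value.

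| b (assumed) | λ | Unadjusted 5%, c = 1.960 | Bonferroni, 3 comparisons, c = 2.394 | Bonferroni, 5 comparisons, c = 2.576 |
|---|---|---|---|---|
| 0 | 0 | 5.0% | 1.7% | 1.0% |
| 0.1 | 0.640 | 9.8% | 4.1% | 2.7% |
| 0.2 | 1.281 | 24.9% | 13.3% | 9.8% |
| 0.3 | 1.921 | 48.4% | 31.8% | 25.6% |

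With all 95 per arm the unadjusted rates are 10.6%, 28.1% and 54.3%. Bonferroni lowers the absolute rates but leaves the shift in place. At 0.2 SD the rate is still about 8 to 10 times its nominal level (13.3 / 1.7 and 9.8 / 1.0).

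These are rates per comparison at one time point, not results of the plan's mixed model. They show how sensitive such a test is to a shift. They do not show that a shift occurred.

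**The case against.** The strongest reply is that the sentence only says how long blinding was assured. It does not say that patients were told their device on that day or later, and in practice the device may have been known only to the theatre team. That stands. A reader might infer that patients were actually unblinded, and the text does not support that inference. It does, however, go beyond silence: it names patients and sets the day of surgery as their end point, so anyone following the rule as written has no duty to keep them unaware afterwards.

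A reader might also infer that the primary endpoint is compromised. The documents do not support that either. Patient knowledge has little direct effect on CT-read union. Blinding of the readers may be described in parts of the document that were not available, so any figure for misreading in one arm would rest on a defect nobody has shown.

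It would also be too broad to say that every comparison is affected. The secondary outcomes are not listed, and some could be intraoperative.

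An unadjusted false-positive rate on its own overstates the absolute risk, because the plan applies Bonferroni. Both sets of rates are therefore given.

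Finally, recruitment ended in February 2018, so a new patient-blinding rule cannot be applied to these patients. That also stands, and it limits the remedy for this trial to disclosure and, where needed, a blinded reading of the CTs.

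**Conclusion.** The point holds in a limited form. The plan gives patients the same blinding end point as the people who must handle the device, so the stated blind does not cover the postoperative clinical outcomes that the plan compares. Followed as written, the rule leaves subjective clinical outcomes open-label with respect to the patient.

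The conclusion about timing rests only on the quoted sentences and needs no assumption. Its practical weight depends on two things the available text does not settle: whether patients and assessors in fact learned the device, and how subjective the clinical outcomes are.

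The size is illustrative: about 10%, 25% or 48% false positives unadjusted for assumed shifts of 0.1, 0.2 or 0.3 SD at 82 per arm, and about 3–4%, 10–13% or 26–32% under Bonferroni with an assumed 3 to 5 comparisons. No size is put on the CT endpoint. This is a cheap improvement worth making, not evidence that the results are biased.

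**What to change.** **Protocol wording.** Split the sentence in two. Surgeons and operating-room staff are blinded until the day of surgery. Patients, and the existing staff who collect clinical scores, stay unaware of the device until the last follow-up, with the device name kept off papers that patients see.

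**Data already collected.** State who was in fact blinded during follow-up: patients, clinical assessors and CT readers. If patients or assessors were not, report the subjective clinical outcomes as unblinded and list this as a limitation. If they were, one sentence settles the matter and strengthens the report.

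**CT reading.** If the rest of the document does not already provide for it, have the existing reader or readers score the 6-month CTs from de-identified images without arm information. The appearance of the gutter may partly reveal the device, and this should be acknowledged.

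**Cost.** Wording, patient papers and de-identification of image files; no extra visit or procedure. The downside is that patients learn their device only after the last follow-up. A re-read assumes that the stored images can be retrieved, and the score collection assumes staff who were not in theatre. The documents confirm neither.

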### Statistical analysis

Continuous data were summarized as mean or median (min, max) values depending on normality. Categorical variables are summarized as frequency (%). The analysis for the primary outcome was performed on data from the intention-to-treat population, which included all subjects who were randomized. Since about 14% of subjects missed the CT to assess bone union at 6 months, multiple imputation was applied. Five multiply-imputed data sets were created using a monotone logistic regression model. The variables in Table 1 were included in the imputation model. A sensitivity analysis was performed with the subjects who received a CT scan at 6 months, who were defined as the per-protocol population. The union rate was compared between the drill group and the UBS group using logistic regression. Because each subject had several laminae, logistic regression with the robust sandwich covariance estimate was used to account for the correlation among laminae within a subject.

Secondary outcomes were compared using the chi-square test for non-continuous values and the t-test or Wilcoxon rank-sum test for continuous values. A linear mixed model was used for clinical outcomes to evaluate between-group differences and changes during each postoperative period compared to the preoperative point, and adjusted p-values were evaluated using the Bonferroni method. The fixed effects were group, time, and the interaction between group and time. All statistical analyses were performed using SAS version 9.4 (SAS Institute, Cary, NC, USA), and statistical significance was defined as  $p < 0.05$  (two-sided).

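### The imputation model for about 27 missing 6-month CTs is not stated to include surgical group; if group was left out, the primary difference shrinks by about 14%

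*Combined protocol and SAP*

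**What the plan says.** All of this is in the combined protocol and SAP.

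- **Missing endpoint.** Statistical analysis: "Since about 14% of subjects missed the CT to assess bone union at 6 months, multiple imputation was applied". The primary analysis covers everyone randomized, so these patients enter it with imputed union status.
- **Imputation.** Five completed data sets come from a monotone logistic method. The only statement about predictors is: "The variables in Table 1 were included in the imputation model".
- **Analysis model.** Union is compared between drill and UBS by logistic regression, with a robust variance because each patient contributes several laminae.
- **Sensitivity analysis.** The comparison is repeated in patients who had the 6-month CT.
- **Postoperative data.** Repeated clinical measurements exist: "A linear mixed model was used for clinical outcomes to evaluate between-group differences and changes during each postoperative period compared to the preoperative point". They are not mentioned as imputation predictors.
- **Planning rates.** Patient population and randomization: "The proportions of fusion failure were assumed to 30% and 10% in laminoplasty with a conventional drill and with a UBS".

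**The concern.** An imputation model should contain every term that the analysis model estimates. Here that term is surgical group. If group is absent, the imputed values are drawn as though group had no effect beyond what the other predictors carry, and randomization makes baseline variables similar across groups. Each arm's missing patients are then filled in near the pooled rate. The observed patients show the full difference, the imputed patients show almost none, and the combined estimate lies between the two.

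The estimate at stake is the primary one. One sentence is all the plan offers to show whether group was a predictor, and that sentence points to a table which normally lists baseline characteristics by group and does not list group itself.

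**Working it through.** **Inputs from the documents.** 190 randomized, 95 per group; about 14% without the 6-month CT; planning failure rates 30% (drill) and 10% (UBS); 80% power, two-sided 5%; 25% drop-out allowance.

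**Step 1: reproduce the plan's own figure.** The plan says "72 patients for each surgical method were required". With mean rate 0.20 and difference 0.20:

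n = [1.96·√(2·0.20·0.80) + 0.8416·√(0.30·0.70 + 0.10·0.90)]² / 0.20² = (1.109 + 0.461)² / 0.04 = 61.6, so 62.

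The continuity correction gives (61.6/4)·[1 + √(1 + 4/(61.6·0.20))]² = 71.3, so 72. The stated figure reproduces. Drop-out: 72/0.75 = 96 against the stated 95, a difference of one patient that has no bearing here. The planning rates are therefore a sound basis for illustration.

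**Step 2: number of patients imputed.** 0.14 × 190 = 26.6, about 27. If 14% is rounded from 13.5% to 14.5%, the range is 25.7 to 27.6. The split by group is not given.

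**Step 3: attenuation if group is omitted.** Let m be the missing fraction in each group and p̄ the pooled observed failure rate. Each group's expected rate after imputation is (1 − m)·p + m·p̄. With m = 0.14 and p̄ = 0.20:

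- drill: 0.86 × 0.30 + 0.14 × 0.20 = 0.286
- UBS: 0.86 × 0.10 + 0.14 × 0.20 = 0.114
- difference: 0.286 − 0.114 = 0.172, which is 0.86 × 0.200
- odds ratio: (0.30 × 0.90)/(0.10 × 0.70) = 3.86 becomes (0.286 × 0.886)/(0.114 × 0.714) = 3.11
- log odds ratio: ln 3.11 / ln 3.86 = 0.841, a fall of about 16%

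The m·p̄ term cancels in the difference, so the shrinkage on that scale is simply the missing fraction.

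**Step 4: uneven missingness.** The 14% overall could be split unequally.

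| Missing, drill / UBS | Failure after imputation | Difference | Odds ratio |
|---|---|---|---|
| 14% / 14% | 28.6% / 11.4% | 17.2 points | 3.11 |
| 5% / 23% | 29.6% / 12.5% | 17.0 points | 2.93 |
| 23% / 5% | 27.5% / 10.5% | 17.0 points | 3.24 |

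The size of the loss hardly depends on the split.

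**Step 5: effect on the test.** Simulation: 10,000 trials, 95 per group, 14% missing completely at random, five imputations combined by Rubin's rules, one binary outcome per patient, no covariates, no lamina clustering.

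| Analysis | Mean difference | Rejection rate |
|---|---|---|
| Imputation with group | 20.0 points | 0.89 |
| Imputation without group | 17.1 points | 0.80 |
| CT-only | about 20 points | 0.90 |
| Imputation without group, both rates 20% | 0 | 0.02 |

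Power with group exceeds 80% because 95 × 0.86 = 81.7 observed patients per group is more than the 72 required.

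**The case against.** The strongest reply is that the omission of group is not established. The sentence on predictors is a statement of what was included; it does not say that nothing else was. Table 1 cannot be seen here, and its absence from the supplied text is not a fault of the plan. This stands, and it makes the whole point conditional. A reader might infer that the reported primary difference is biased toward zero. The documents do not support that as fact.

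Second, the consequence is limited. With no true difference, omitting group makes the test conservative, and simulated power of about 0.80 still meets the planned level. Both are correct within the simulation. But the trial enrolled more than it needed, and the omission would spend that margin. It would also understate the effect estimate whatever the test shows.

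Third, the CT-only analysis involves no imputation and recovers the full difference in the simulation. That is a useful check, and a gap between the two analyses would be a warning sign. It can stand in for the primary result only if CTs are missing completely at random, and it does not repair the intention-to-treat estimate.

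Two further inferences are tempting and should not be drawn. One is that leaving out postoperative data also pulls the difference toward zero. It may cost precision and make missing-at-random harder to defend, but its bias has no fixed direction. The other is that scans at other times were ignored and could settle the missing values. The supplied text mentions no CT except the one at 6 months, the postoperative periods it describes concern clinical outcomes, and nothing in it supports treating union as irreversible.

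**Conclusion.** The point holds in conditional form. The plan does not state that surgical group is in the imputation model for about 27 patients' primary endpoint. If Table 1 is a baseline table and group was therefore left out, imputation and analysis models are incompatible. The expected difference then shrinks by about 14% of itself (2.8 points, from 20.0 to 17.2) and the odds ratio falls from 3.86 to 3.11. The direction is conservative: an understated effect and lost power, with no inflation of false positives. If group was included, this attenuation is absent and only a clarifying sentence is needed.

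The figures assume that the planning rates are the true rates, that the other predictors do not differ by group, and that patients with missing CTs contribute about as many laminae as the rest. The power figures also ignore clustering of laminae within patients and are illustrative only.

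**What to change.** In the Statistical analysis section, replace the sentence on predictors with: *The imputation model includes surgical group and the Table 1 variables.* If group was not in the model that was run, re-run the primary intention-to-treat analysis with it. The cost is one term in the SAS imputation code and one re-run, with no new data. If group was already included, the cost is the sentence alone.

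An optional addition is to use the postoperative clinical scores already collected as auxiliary predictors, for precision and to make missing-at-random more plausible. How well they predict union is not shown in the documents, so the gain may be small. Missing scores would have to be imputed as well. If the resulting pattern is not monotone, the planned monotone method no longer fits, and a non-monotone method such as fully conditional specification is needed.

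### Should the primary logistic regression for union have been adjusted for baseline covariates?

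*Combined protocol and SAP*

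**What the plan says.** The relevant statements are in two sections of the combined protocol and SAP.

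- **Primary model (Statistical analysis):** "The union rate was compared between the drill group and the UBS group using logistic regression". Clustering is covered: "logistic regression with the robust sandwich covariance estimate was used to account for the correlation among laminae within a subject". No terms are listed for this model. The same section does list the fixed effects of the mixed model for clinical outcomes (group, time and their interaction). An unadjusted model is therefore the natural reading, but it is inferred.
- **Missing outcome (Statistical analysis):** "Since about 14% of subjects missed the CT to assess bone union at 6 months, multiple imputation was applied". The method is given as "Five multiply-imputed data sets were created using a monotone logistic regression model", and "The variables in Table 1 were included in the imputation model". Baseline variables thus have a stated role, but only in imputation. The one sensitivity analysis restricts to subjects with the 6-month CT and names no covariate.
- **Eligibility and design (Patient population and randomization):** patients have "cervical myelopathy at 3 or more levels due to spondylosis, congenital stenosis, or OPLL" and are "aged more than 20 years", so age, cause of myelopathy and number of levels are known before surgery. Allocation uses variable blocks, and no stratification factor is named. The sample size rests on this: "The proportions of fusion failure were assumed to 30% and 10% in laminoplasty with a conventional drill and with a UBS".

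**The concern.** Adjusting for a baseline variable that predicts outcome usually sharpens a randomised comparison at no cost in data. Here age, diagnosis and number of levels are available for every patient, and baseline variables are already trusted enough to drive the imputation, yet the primary model appears to contain group alone. If one of these variables predicts union strongly, the analysis leaves some precision unused: a wider interval for the difference in union rates and possibly lower power.

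**Working it through.** **1. The plan's own sample size.** Inputs from Patient population and randomization: failure 0.30 and 0.10, two-sided 0.05, power 80%.

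n = [1.96·√(2·0.2·0.8) + 0.8416·√(0.3·0.7 + 0.1·0.9)]² / 0.20² = 61.6

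With continuity correction: (61.6/4)·[1 + √(1 + 4/(61.6·0.20))]² = 71.25, rounded up to 72 per arm as stated. Dividing by 0.75 gives 95 from the unrounded value or 96 from 72; the plan states 95. The trial was therefore sized for an unadjusted comparison of two proportions and does not count on covariates for its power.

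**2. What a given narrowing requires.** If covariates explain a share R² of the outcome variance, the standard error shrinks by s = 1 − √(1 − R²). So s = 5% needs R² = 1 − 0.95² = 0.098, and s = 10% needs R² = 1 − 0.90² = 0.19. The documents give no R², so both values are assumptions.

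**3. Patient-level power at the planned effect.**

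Power = Φ{[0.20 − 1.96·(1 − s)·√(0.32/n)] / [(1 − s)·√(0.30/n)]}

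| n per arm | s = 0 | s = 5% | s = 10% |
|---|---|---|---|
| 72 | 85.9% | 89.2% | 92.2% |
| 82 (95 × 0.86 with CT) | 90.0% | 92.7% | 95.0% |
| 95 | 93.8% | 95.7% | 97.3% |

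The gain at s = 10% is about 4 to 6 points without continuity correction. With it, the gain at 72 per arm is 80.5% to 88.1%, about 8 points.

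**4. Lamina-level power, the analysis the plan describes.** With m laminae per subject, the effective n per arm is n·m / [1 + (m − 1)·ICC]. Neither m nor the ICC is given. For 82 per arm and an assumed m = 4:

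| ICC (assumed) | effective n | full 95% CI width, union difference | power, s = 0 | power, s = 10% |
|---|---|---|---|---|
| 0.1 | 252 | 13.5 points | 99.99% | 100.0% |
| 0.3 | 173 | 16.3 points | 99.7% | 99.95% |
| 0.5 | 131 | 18.7 points | 98.5% | 99.6% |
| 0.7 | 106 | 20.9 points | 95.8% | 98.4% |
| 0.9 | 89 | 22.8 points | 92.1% | 96.4% |

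Up to ICC 0.5 there is almost nothing to gain. The gain reaches about 3 to 4 points only when laminae in one subject behave almost alike and R² is also near 0.19.

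**5. Simulated narrowing of a standardised risk difference.** Assumptions: 95 per arm, 14% of subjects without CT, five imputations, 4 laminae, failure 30% versus 10%, and one covariate with log-odds 0, 0.4, 0.7 or 1.0 per SD.

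- Subject SD 1.0: 0, 2, 6 and 10% narrower; the largest change in full width is from 15.1 to 13.6 points.
- Subject SD 2.0: 0, 1, 2 and 5% narrower; the largest change is from 17.3 to 16.5 points.

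Power was at least 99.4% with and without adjustment. In complete cases the narrowing reached 12% with 4 laminae and 13% across 3 or 5. Diagnosis and number of levels were simulated as non-prognostic, so these figures show no gain from those two variables.

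**6. The scale of the planned model.** Logistic regression estimates a log odds ratio. Adjusting for a prognostic covariate changes that target to a conditional odds ratio, and its standard error need not fall. In simulation the ratio of adjusted to unadjusted standard error was 0.98 to 1.01 at lamina level. At patient level it rose by about 3, 8 and 14% at covariate log-odds 0.5, 0.9 and 1.2 per SD. The narrowing in step 5 therefore belongs to a standardised difference in union rates, which the Statistical analysis section does not mention and which would have to be added.

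**The case for a change.** The best case for adjustment is that it is cheap, that the range of narrowing is reproducible, and that it can help. Much of that stands. An independent patient-level simulation gave about 0, 2, 6 and 9% narrowing of the standardised difference at covariate log-odds 0, 0.5, 0.9 and 1.2 per SD. Nor would it be right to say that power cannot rise at the planned effect. On a patient-level reading, which matches how the trial was sized, simulated power at 72 per arm went from 86.7% to 90.0% at log-odds 1.0. Power can rise even where the standard error of the log odds ratio widens, because the conditional estimate moves further from zero: at 82 per arm and log-odds 1.2 it went from 91.0% to 95.3%.

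This shows that adjustment can be useful, not that its absence is a defect. Each gain depends on a prognostic strength that the documents do not supply, and it is zero if no covariate predicts union. There are also costs:

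- Adjusted type I error with the plain sandwich was 4.5 to 6.2% under imputation (unadjusted 3.9 to 6.5%), so roughly 5 to 7% would have to be allowed for.
- On a patient-level reading, a sparse diagnosis category left unmerged (10% of patients, assumed) made 5.0 to 6.2% of fits fail and lowered adjusted power by 2.2 to 4.3 points.
- Timing is against it. The text is in the past tense, recruitment has ended and the share of missing CTs is known. A covariate list chosen now could probably not be shown to precede the union results, so the adjusted model would have to be a labelled sensitivity analysis. That leaves the primary test and its power exactly as they are.

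**Conclusion.** The concern does not hold. The unadjusted comparison is valid under randomisation, within-subject correlation is handled by the sandwich variance, no named stratification factor calls for a covariate, and the stated sample size is reproduced without any allowance for adjustment.

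The possible benefit is 0 to 10% off the width of a standardised risk-difference interval in the imputed data (up to 13% in complete cases), under assumed covariate log-odds of 0 to 1.0 per SD. At the planned effect it brings almost no lamina-level power up to an ICC of about 0.5, about 3 to 4 points at ICC 0.7 to 0.9, and at most about 4 to 8 points on a patient-level reading with R² of 0.19. The number of laminae, the ICC and the prognostic strength are all assumptions.

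An adjusted model is a legitimate preference. Its absence biases nothing, and adding it at this stage as a sensitivity analysis would not alter the primary test.
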